5 COMPLICATIONS

In addition to the standard operating procedures for reporting complications per hospital/physician protocol, all clinical events, including both observed or volunteered problems, complaints, symptoms, physical signs or disease which either occur during the study, having been absent at baseline, or, if present at baseline, appear to worsen during the clinical outcomes collection study are to be recorded as complications in the subject's medical record and on the appropriate case report form.

Complications reported in the literature as most commonly associated with interbody and posterolateral lumbar fusion procedures include, but are not limited to, infection, nerve damage, blood clots, blood loss, and bowel and bladder problems, along with complications associated with anesthesia. A potential risk inherent to spinal fusion is failure of the vertebral bone and graft to properly fuse, a condition that may require additional surgery.

5.1 Definitions

A complication is any written, electronic, or oral communication that alleges deficiencies related to the identity, quality, durability, reliability, safety, effectiveness, performance, or any indication of the failure of a medical product to meet a user or customer's expectations. The complication may be the possible failure of a device or tissue product, labeling, or packaging to meet any of its specifications after it is released for distribution.

6 STATISTICAL ANALYSIS PLAN

Statistical analyses will be performed as deemed appropriate to evaluate fusion outcomes across the groups.

An interim analysis may be performed once, at minimum, half of the subject accrual is met. In the case early findings show a statistical difference between the two studied cages, enrollment will cease as investigators are unlikely to maintain clinical equipoise to continue to randomize patients. Similarly, if the interim analysis suggests it is unlikely the study will achieve statistical significance, the investigators may choose to close the trial early for futility. Currently enrolled subjects will be followed throughout the remainder of the study, up to 12 months post-surgery.

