3 TRIAL DESIGN

3.1 Design

The randomized controlled trial will prospectively evaluate the safety and efficacy of the Nexxt Matrixx[™] System titanium implant supplemented with a pedicle screw system as compared to a representative PEEK cage currently used in routine fashion for lumbar interbody fusion procedures. This study will capture clinical and radiographic outcomes on patients up to 2 years post operatively. Both cages will be used in conjunction with milled local autograft bone generated as part of the spinal fusion procedure (no iliac crest autograft will be utilized).

This single centered study will enroll up to 70 subjects (n = 35 per group), with subjects followed for a minimum of 12 months post-surgery. All subjects enrolled in the study will be recruited from a pool of subjects eligible for combined interbody/posterolateral lumbar fusion surgery. The inclusion/exclusion criteria are listed below.

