4.6 Independent Radiographic Assessment

An independent radiographic analysis will be performed to evaluate all images and assess subjects' radiographic status. The independent radiographer will receive deidentified disks and will not have access to any personally identifiable information. The following quantitative and qualitative assessments will be performed.

Fusion Determination

Fusion will be assessed by an independent radiographer when data collection is complete. X-rays at each visit and a lumbar CT at 6 months will be evaluated for fusion determination. Interbody fusion will be graded by the method of Brantigan and Steffee as modified to describe the Fraser definition of locked pseudoarthrosis (BSF scale) (Santos et al., 2003). The grading system is as follows:

- BSF-1: Radiographical pseudarthrosis
- BSF-2: Radiogaphical locked pseudarthrosis
- BSF-3: Radiographical fusion

Radiographic Success: Radiographic success is defined by radiographical fusion (BSF-3) presenting bone bridges within at least half of the fusion area with at least the density originally achieved at surgery.

Radiographic Failure: Radiographic failure is defined by radiographical pseudarthrosis (BSF-1 or -2)

X-rays will be uploaded into the REDCap as a JPEG image at each subject visit.

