4.7 Success Criteria

4.7.1 **Primary Measure of Effectiveness**

A subject will be considered a success if fusion is a Grade BSF-3 at 6 months. The primary outcome measure of effectiveness will be determined by the fusion rate at 6 months post-operatively in subjects implanted with either titanium cage as compared to the PEEK cage.

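### Section 6 makes enrollment cease on an undefined statistical difference at an optional interim look, with no test, level, boundary or post-stop analysis rule, and Section 4.6 schedules no independent fusion grades for that look

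*Combined protocol and SAP*

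**What the plan says.** - **Size and outcome.** Section 3.1: "This single centered study will enroll up to 70 subjects (n = 35 per group". Section 4.7.1 defines the primary outcome: "A subject will be considered a success if fusion is a Grade BSF-3 at 6 months".
- **Method.** Section 6 has one general sentence: "Statistical analyses will be performed as deemed appropriate to evaluate fusion outcomes across the groups".
- **Interim look.** Section 6: "An interim analysis may be performed once, at minimum, half of the subject accrual is met". The look is optional, and half of accrual is its earliest time.
- **Efficacy stop.** "In the case early findings show a statistical difference between the two studied cages, enrollment will cease". The reason given is that investigators would be unlikely to keep equipoise. The stop is worded as mandatory.
- **Futility stop.** This one is discretionary: "if the interim analysis suggests it is unlikely the study will achieve statistical significance, the investigators may choose to close the trial early for futility".
- **After a stop.** "Currently enrolled subjects will be followed throughout the remainder of the study, up to 12 months post-surgery". This covers follow-up. Nothing is said about analysis.
- **Fusion reading.** Section 4.6: "Fusion will be assessed by an independent radiographer when data collection is complete".

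The documents state no alpha, sidedness, power, expected fusion rates or accrual period.

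**The concern.** A mandatory action depends on an event that the plan does not define. Two careful analysts with the same interim data could reach opposite decisions, one using chi-square at 5% and the other Fisher's test or a stricter level.

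Three consequences follow.

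- If a nominally significant interim result is reported as the trial's finding, and the final test is also run at 5%, there are two chances of a false positive.
- If the later data on all enrolled subjects are to decide, enrollment may have ended on a signal those data do not support. The plan has no rule for that case.
- The interim needs 6-month fusion grades, but the trigger counts enrolled subjects, and the independent grades are scheduled for a time after the interim would take place. Sections 4.6 and 6 must be reconciled before the look can be carried out on the primary outcome.

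**Working it through.** **The plan's own figure.** The only design figure is 70 subjects, 35 per group. It cannot be reproduced, because no alpha, power, fusion rates or dropout are given.

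**Assumptions.** Two-sided 5% at each look; a look at 18 v 17 six-month outcomes; a final analysis at 35 v 35; a common fusion rate of 50-90% under no difference; uniform accrual of 70 subjects over A months.

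**Step 1, timing.** When the 35th subject enrolls, the number with a 6-month outcome is 70 × (A/2 − 6)/A.
- A = 18: 70 × 3/18 = 11.7
- A = 24: 70 × 6/24 = 17.5
- A = 36: 70 × 12/36 = 23.3

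The earliest permitted look would therefore have about 12 to 23 outcomes (17% to 33% of 70), and none if accrual took 12 months. When the 35th outcome arrives, the number enrolled is 70 × (A/2 + 6)/A, which is about 58, 53 or 47.

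**Step 2, type I error if the interim test is the claim.** In large samples this is 1 − P(|Z1| < 1.96 and |Z2| < 1.96), with correlation √t at information fraction t. At t = 0.50 it is 8.3%; at 0.25, 9.1%; at 0.75, 7.3%.

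The exact version sums binomial probabilities: P(reject at 18 v 17) + P(no rejection then, reject at 35 v 35).

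| Common fusion rate | Chi-square, two looks | Chi-square, one look | Fisher, two looks | Fisher, one look |
|---|---|---|---|---|
| 50% | 7.2% | 4.3% | 5.6% | 2.4% |
| 60% | 7.9% | 4.8% | 5.6% | 2.8% |
| 70% | 8.5% | 5.1% | 5.1% | 2.8% |
| 80% | 8.4% | 4.9% | 4.9% | 2.5% |
| 90% | 7.7% | 5.7% | 2.8% | 1.3% |

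In steps of 5 points over 50-90%, the ranges are 7.2-8.5% against 4.3-5.7% (chi-square) and 2.8-5.6% against 1.3-2.9% (Fisher).

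**Step 3, type I error if the claim is retested at 5% on all enrolled after a stop.** The sum becomes P(stop and significant on all enrolled) + P(no stop and significant at 35 v 35). The result is 4.7-6.5% with chi-square and 1.3-3.8% with Fisher. These ranges cover looks at half accrual with 35 enrolled, and looks at 35 outcomes with 47 to 58 enrolled.

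**Step 4, stops that later data do not confirm.** The unconfirmed share is 1 − P(stop and significant on all enrolled)/P(stop). Assume true fusion of 85% v 65%.
- Chi-square at 18 v 17: 28% of trials stop, and 14-17% of those stops are not significant on the 47 to 58 enrolled. As a share of all trials this is 0.28 × 0.14 = 3.9% to 0.28 × 0.17 = 4.8%.
- Fisher at 18 v 17: 23% stop, and 26% of those are unconfirmed with 52 enrolled. This is 0.23 × 0.26 = 6.0% of all trials.
- Chi-square at the earliest permitted look (12 to 23 outcomes, 35 enrolled): 23-38% of stops are unconfirmed.

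**Step 5, with a boundary.** An O'Brien-Fleming-type Lan-DeMets boundary at 50% information has nominal p of 0.0031 at the interim and 0.0490 at the end. With chi-square at 18 v 17, and a retest at 0.0490 after a stop, exact error is 4.3-5.7%, the same as for one look. Unconfirmed stops fall to 1-3% of stops.

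**The case against.** The strongest reply is that Section 6 does not call the interim test the trial's claim. It ends enrollment because equipoise is lost, and it keeps following those enrolled. On that reading inflation is small with chi-square, and Fisher's error stays below 5%. Material inflation needs an assumed level, an assumed chi-square test and an assumed claim rule. This stands, and it limits what can be said about size.

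Several stronger statements are tempting, and the documents do not support them.

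- **That the plan has an error rate of 8% or more.** No single figure can be attributed to it, because the test and the claim rule are unstated.
- **That repeated interim looks are planned.** The interim sentence reads naturally as meaning as soon as half of accrual is reached, and it speaks of one analysis. No maximum is stated, but nothing supports two interim looks.
- **That nothing is laid down after a stop.** Follow-up is laid down. The analysis rule is what is missing.
- **That fusion is looked at only at the end.** Section 4.6 schedules the independent reading then. Section 4.5 has the investigator assess progress towards fusion at each visit, although nothing makes that assessment the BSF grade or the basis of the interim.
- **That any look must have less than half of the information.** Half of accrual is a minimum, so a later look could have 35 or more outcomes.

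None of this supplies a threshold, a test or an analysis rule, or removes the timing conflict between Sections 4.6 and 6.

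**Conclusion.** The concern holds in bounded form and should be fixed before any interim look. The textual part needs no assumptions: a mandatory enrollment stop rests on an undefined criterion, its trigger is not tied to 6-month outcomes, the analysis after a stop is unspecified, and no independent grades are scheduled for it.

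The numerical part is conditional on 5% at each look. With the interim test as the claim, chi-square gains roughly 2 to 3.6 points of type I error over one look, while Fisher roughly doubles but does not exceed 5.6%. With a retest on all enrolled, the remaining problem is mainly unconfirmed stops, whose frequency rests on the assumed 85% v 65%. Because the look is optional, no harm arises if it is never used.

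**What to change.** In Section 6:

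1. State an overall two-sided alpha of 0.05 and name one test of 6-month BSF-3 for both looks. Chi-square and Fisher are both defensible.
2. Allow at most one efficacy look, triggered by at least 35 subjects with a 6-month fusion grade.
3. Stop for efficacy only if a prespecified alpha-controlling boundary is crossed. Examples at 50% information are Lan-DeMets O'Brien-Fleming-type (0.0031 and 0.0490) or classical O'Brien-Fleming (0.0052 and 0.0480). The choice is the sponsor's.
4. State which analysis is the trial's result after a stop, and always report the 6-month outcomes of all randomised subjects. Requiring that analysis also to be significant is optional and is not needed for alpha control. Its handling of withdrawals must be made consistent with Section 4.8, which leaves some withdrawals out of success and failure.

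In Section 4.6, have the same independent radiographer grade the available 6-month images before the interim. The futility stop can stay discretionary.

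**Simpler alternative:** drop the interim efficacy test and test once at 5%.

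**Cost.** The change is wording plus one earlier reading batch. From 80% in large samples, power falls by about 0.2 points (look at 50%) to 1.4 points (look at 75% with the retest). At 85% v 65% with chi-square, early efficacy stops fall from 28% to about 5% of trials. With 47 to 58 subjects already enrolled at the 35th outcome, a stop then saves only 70 − 58 = 12 to 70 − 47 = 23 subjects, which makes the simpler alternative reasonable.

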4.2 Randomization

All subjects will be randomized in the trial to receive either the Nexxt Spine Nexxt MatrixxTM 3D-printed titanium cage or the HonourTM PEEK cage supplemented with a pedicle screw system and milled local autograft bone. Subject randomization will be stratified according to smoking status. Subjects will be blinded to their group status for the duration of the study assessments and procedures (12 months post-operatively).

4.3 **Perioperative and Postoperative Management**

Surgeons will perform combined interbody and posterolateral lumbar fusion utilizing either Nexxt MatrixxTM or PEEK cages supplemented with a pedicle screw system cleared for fusion and milled local autograft bone (per customary protocol).

Data will be collected during and immediately after the surgery according to the parameters described by the Nexxt Matrixx[™] IF/PLF CRFs. This includes: diagnosis, duration of surgery, blood loss, OR time, length of hospital stay, instrumentation used, type of procedure, and surgical level(s). In addition, all intra-operative complications (e.g. excessive blood loss, hematoma, vascular injury, etc.) will be reported and recorded as a complication on the CRF.

Intra-operative (after hardware installation is completed) or immediate postoperative x-rays will be obtained. Postoperative care will follow the standard of care at each institution for subjects who undergo fusion procedures.

Postoperative care is extremely important. The subject should be warned that noncompliance with postoperative instructions could lead to breakage of the pedicle screw system and/or possible migration requiring revision surgery to remove the pedicle screw system.

Screening/	Procedure	3 months	6 months	12 months	24 months
Enrollment		(± 7 days)	(± 14 days)	(± 30 days)	(± 60 days)
procedure)					
Х					
Х					
Х					
Х	Х	Х	Х	Х	X**
	Х				
Х		Х	Х	Х	X**
X		Х	X	Х	X**
X		Х	X	Х	X**
			X*		
Х	Х	Х	Х	Х	X**
	Enrollment (-60 days of procedure) X X X X X X X X X X X X	Enrollment (-60 days of procedure) X X X X X X X X X X X X X X X	Enrollment (-60 days of procedure)(± 7 days)X	Enrollment (-60 days of procedure)(± 7 days)(± 14 days)XXX	Enrollment (-60 days of procedure) $(\pm 7 days)$ $(\pm 14 days)$ $(\pm 30 days)$ X </td

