4.8 Subject Withdrawal

It is recognized that the subject's participation in this trial is entirely voluntary, and that she/he may refuse to participate and may withdraw from participation at any time without jeopardy to any future medical care. It is also recognized that the investigator, at his/her discretion, may withdraw a subject from this study based upon his/her professional judgment.

Other Conditions for Withdrawal:

Any subject who develops a severe concurrent medical illness during the trial should be withdrawn. This type of illness is defined as any illness that would hinder the subject's ability to return for scheduled follow-up appointments. Such a withdrawal will not be counted for the purposes of determining success or failure.

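### The investigators who randomise and may withdraw subjects decide futility on an undefined criterion, with no limit on who sees the interim comparison

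*Combined protocol and SAP*

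**What the plan says.** Section 6 contains the whole interim plan.

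- **Timing:** "An interim analysis may be performed once, at minimum, half of the subject accrual is met". The look is optional and tied to accrual.
- **Efficacy:** on a statistical difference, "enrollment will cease as investigators are unlikely to maintain clinical equipoise to continue to randomize patients".
- **Futility:** if the look suggests that significance is *unlikely*, "the investigators may choose to close the trial early for futility".

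No conditional-power threshold, boundary, significance level or assumed effect is given. No monitoring committee, separate statistician or limit on access to interim results is described.

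Other sections bear on the point:

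- Section 3.1: a single-centre trial of up to 70 subjects, 35 per group.
- Sections 3.2 (criterion 4) and 3.3 (criteria 9 and 11): eligibility rests partly on the investigator's opinion.
- Section 4.2: subjects are blinded to 12 months. No blinding of investigators or surgeons is described.
- Section 4.5: the investigator carries out the follow-up examinations.
- Section 4.6: an independent radiographer grades fusion from de-identified images, once data collection has finished.
- Section 4.7.1: the primary endpoint is BSF-3 fusion at 6 months.
- Section 4.8: "the investigator, at his/her discretion, may withdraw a subject from this study based upon his/her professional judgment".

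**The concern.** Two things are at stake.

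**Conduct after the look.** The stated reason for an efficacy stop makes sense only if the investigators are told the comparison. If the trial continues, they go on judging eligibility, randomising, examining and, at their discretion, withdrawing subjects. Someone who knows the trend can, without intending to, apply these judgements differently.

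**The futility decision.** The word *unlikely* has no number attached, and the choice belongs to the same people. Different reasonable readings give very different chances of closing a trial of a cage that truly works better. The plan therefore cannot state its own power once a look is taken.

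**Working it through.** **The plan's own figure.** The only design figure is 70 subjects (35 per group). It cannot be reproduced, because no significance level, power, fusion rate or effect is stated. Everything below rests on assumptions.

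**Exposure.** The look comes at 35 of 70 or later, so at most 70 − 35 = 35 subjects are randomised after it. The resulting bias cannot be calculated from the documents.

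**Futility, normal approximation.** Assumptions: two-sided 0.05; a real effect for which the full trial has 80% power, so the expected final Z is θ = 1.96 + 0.84 = 2.80; no efficacy stop. Let t be the fraction of information at the look. If all 35 subjects have a 6-month grade, t = 0.5. If accrual outruns follow-up and only 21 do, t = 21/70 = 0.3. The accrual rate is not stated, so both are shown.

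Conditional power (CP) on the current trend falls below a chosen level when Z₁ is below

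c = √t × [1.96 + Φ⁻¹(CP) × √(1 − t)].

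Since Z₁ has mean θ√t, P(stop) = Φ(c − θ√t). Remaining power is P(Z₁ ≥ c and final Z ≥ 1.96), with correlation √t.

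- t = 0.5, CP 50%: c = 0.707 × 1.96 = 1.386; mean 1.981; Φ(−0.595) = 0.276.
- t = 0.5, CP 10%: c = 0.707 × (1.96 − 1.282 × 0.707) = 0.745; Φ(−1.236) = 0.108.
- t = 0.3, CP 50%: c = 0.548 × 1.96 = 1.073; mean 1.534; Φ(−0.461) = 0.322.
- t = 0.3, CP 10%: c = 0.548 × (1.96 − 1.282 × 0.837) = 0.486; Φ(−1.048) = 0.147.

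| Information | Stop if CP below | Real-effect trials stopped | Power left (from 80%) |
|---|---|---|---|
| 0.5 | 50% | 28% | 66% |
| 0.5 | 10% | 11% | 77% |
| 0.3 | 50% | 32% | 60% |
| 0.3 | 10% | 15% | 73% |

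**Exact binomial check.** Interim at 17 or 18 per arm with all grades known, final at 35 per arm, pooled z-test, and assumed fusion rates of 60 v 85%, 60 v 90%, 50 v 80% and 70 v 95%.

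| CP computed under | Stop if CP below | Stopped despite the effect | Power lost (points) |
|---|---|---|---|
| Current trend | 10% | 6.5–16% | 2.3–3.8 |
| Current trend | 50% | 20–36% | 10.0–12.9 |
| Assumed effect | 10% | 0.2–2.9% | at most about 0.1 |
| Assumed effect | 50% | 5–23.5% | 1.5–6.0 |

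Across these readings of one word, wrongful stopping runs from about 0.2% to 36%.

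**Type I error.** Futility stopping alone does not inflate it (0.048 falls to 0.041 at equal rates of 60% with a current-trend cut-off of 20%). Testing at 0.05 at both looks does: 0.080 to 0.085 by exact calculation, for equal rates of 50% to 80% and 17 per arm at the interim.

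**The case against.** The strongest reply is that Section 6 does not say who runs the look, what is released or to whom, and that the trial has safeguards. Much of this stands, and it rules out several stronger readings.

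- *The rest of the trial is biased.* The documents support only that it can be. The look is optional, subjects are blinded, and the investigators do not assign the primary grade. One gap remains: masking of the radiographer to cage type is not stated.
- *The plan states that the investigators see the comparison.* This is a strong inference from the equipoise sentence, not text.
- *The investigators operate.* Section 4.3 says only "Surgeons will perform combined interbody and posterolateral lumbar fusion". That the surgeons are the investigators is likely at one centre but not stated.
- *ODI and VAS would be contaminated.* Subjects complete these forms themselves and are blinded to 12 months, and neither scale is a success criterion in Section 4.7.
- *Investigators could raise a fusion rate by withdrawing unfused subjects.* In Section 4.8, "Such a withdrawal will not be counted for the purposes of determining success or failure" refers to withdrawal for severe concurrent illness. How discretionary withdrawals are counted is not stated, so no shift in the rate can be derived.
- *The rule will discard a real effect.* Any futility rule sometimes does. The 50% reading is one interpretation of *unlikely*, and the text makes stopping optional.

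What survives is that the criterion has no value, the decision rests with those who randomise, and nothing limits access to the results.

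**Conclusion.** The concern holds in this limited form. Section 6 leaves futility to the investigators on an undefined criterion and implies that they learn the comparison, with no restriction on access. If the look is taken and the trial continues, later enrolment, withdrawal and investigator-rated assessments can be biased for up to 35 of 70 subjects, by an amount that the documents do not allow anyone to compute.

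The risk of stopping despite a real effect is uncontrolled. At an assumed 80% full-trial power with current-trend conditional power, it ranges from 11% to 32% over the four cases worked, and power falls to between 77% and 60%. Even a 10% current-trend cut-off is not cheap if the look comes early: 15% stopped and 73% power at 30% of the information. These figures illustrate the spread; they are not predictions for this trial.

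**What to change.** Rewrite the interim paragraph of Section 6, and amend Section 4.6 to match.

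1. **Who:** a designated person already on the study who does not enrol, operate, follow up or grade images runs the single look. The documents name no analyst, so this role must be assigned.
2. **When:** once a stated number of subjects have a 6-month grade, rather than at a share of accrual. Amend Section 4.6 so that the independent radiographer reads those images before the look; as written, no independent grades would exist then.
3. **What is released:** only *stop* or *continue*. Interim rates and p-values stay closed until the last 12-month visit.
4. **Futility rule, fixed beforehand:** a non-binding threshold, for example conditional power below 10%, preferably under a stated design effect. In the exact calculations that version cost at most about 0.1 point of power.
5. **Efficacy boundary, fixed beforehand:** one that controls overall type I error without relying on futility stops, since two looks at 0.05 give about 8%.

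This needs no added subjects, visits or committee. The costs are that the investigators lose discretion over the interim decision and some image reads move earlier.
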